Thus, it remains to show if prolonged adjuvant IPC therapy during the whole 6 weeks immobilization period could reduce the incidence of VTE in leg-immobilized patients, also in patients with fractures. Can the IPC treatment synchronously enhance the healing process so that it will lead to a long-term increased patient-reported outcome? Recent studies suggest that the increased neuro-vascular flow induced by IPC enhances the healing process¹⁵.

Research question

The primary research question is:

- Does addition of IPC to patients with lower limb immobilization in routine care, reduce the incidence of VTE up to the end of immobilization, i.e. 6-8 weeks.

Secondary questions are:

- Can adjuvant IPC during leg immobilization enhance fracture/soft tissue healing and improve patient-reported outcome?
- Does IPC reduce VTE incidence by upregulation of profibrinolysis?

Variables and measures

Primary outcome (binary), VTE, is defined as symptomatic or asymptomatic deep venous thrombosis (DVT) assessed at six weeks of immobilization by screening compression duplex ultrasound (CDU), or symptomatic pulmonary embolism detected by computer tomography. Assessors of CDU will be skilled ultrasonographers, masked to the treatment allocation⁹. The CDU-examination will document absence/presence of thrombus in the calf, popliteal and femoral veins separately, as previously described⁹. All positive examinations and those considered technically difficult will be reviewed by a specially trained vascular physician (blinded to the treatment allocation), who will establish the diagnosis and classify the examination result as absence or presence of thrombus. This will show the incidence of VTE in each group.

We acknowledge that the CDU assessment of DVT will be the dependent measure of outcome since DVT is more common than pulmonary embolism. CDU screening (surrogate outcome), can be justified because of the clinical significance attributed to even asymptomatic DVTs, which today are known to cause a high rate of pulmonary embolism, affect the patient outcome¹⁶ and are treated by most clinicians with anticoagulant therapy¹⁰. To reliably confirm or refute an effect of IPC on survival or clinical pulmonary embolism a

randomized trial would require a sample size of several tens of thousands of patients; this is not currently possible.

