Is IPC more effective in patients at higher risk of DVT? It seems likely that patients at higher risk of DVT might gain greater benefit from IPC than those at lower risk. Patients with ATR exhibit higher risk of DVT than patients with AF, and patients aged ≥ 40 years exhibit almost fivefold higher odds of developing DVT⁹. Moreover, prior history of DVT, weight-bearing, and surgery are likely to affect the risk of DVT. Therefore, we will undertake subgroup analyses of the effect of allocation to IPC on the primary outcome among patients with and without at least one of these factors at baseline.

Analysis of impact of delay in applying IPC? There is often a delay in presenting or being treated with a lower limb injury (ATR/AF) and therefore this can lead to a delay in applying VTE prophylaxis. Moreover, patients may even suffer a VTE before treatment is initiated. Thus, we hypothesize that IPC will reduce the frequency of the primary outcome to a greater

extent among patients enrolled early compared to later. We will therefore examine the effect of treatment among patients enrolled early versus later after injury.

Compliance and duration of treatment with IPC? IPC compliance was 91% in our recent trial, but has usually been used for a relatively short time on perioperative patients and in outpatients. There is a concern that IPC may not be used for the whole six weeks or that it will not be applied continuously. We will therefore carry out additional analyses in order to determine how IPC-compliance affects the primary outcome.

Economic analyses: Economic analysis of the trial treatment effects will involve a within-trial evaluation of cost effectiveness integrated into a decision-analytic model of longer run costs and health effects. The within-trial analysis will be conducted on an intention-to-treat basis. The primary health endpoints will be VTE times adjusted for patient reported outcome.

A societal perspective will be taken for assessing costs of patient's care during the six-week immobilization. Patient-specific hospital resource use will be measured. The net direct medical cost will include a cost estimate of IPC capital/equipment (and staffing implications) and the averted costs arising from the effects of IPC on expected DVT/PE incidence. Probabilistic sensitivity analysis will also be used to assess the hospital cost distributions.

Specific intermediate objectives

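### The primary outcome allows only absence or presence of thrombus, so incompletely seen scans must be given a definite result, and thrombus that predates randomisation can count as incident VTE

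*Combined protocol and SAP*

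**What the plan says.** The section Variables and measures sets out the endpoint as follows: "Primary outcome (binary), VTE, is defined as symptomatic or asymptomatic deep venous thrombosis (DVT) assessed at six weeks of immobilization by screening compression duplex ultrasound", with symptomatic pulmonary embolism on computed tomography as the other route to an event. The definition does not require the thrombus to be new.

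The recording rule is two-valued at both levels. By vein: "The CDU-examination will document absence/presence of thrombus in the calf, popliteal and femoral veins separately, as previously described". By scan: "All positive examinations and those considered technically difficult will be reviewed by a specially trained vascular physician", blinded to allocation, "who will establish the diagnosis and classify the examination result as absence or presence of thrombus". The plan states no minimum set of segments that must be seen, no repeat-scan rule after a difficult scan, and no missing-data rule for a non-diagnostic one. The Statistical analysis plan adds nothing on this.

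On thrombus present before treatment:

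- The research question concerns the incidence of VTE up to the end of immobilization.
- Under Material: Patient selection, treatment may start up to 10 days after injury. The exclusion list contains neither prior DVT nor a VTE diagnosed since the injury.
- The Statistical analysis plan names prior DVT as a risk factor for a subgroup analysis: "Moreover, prior history of DVT, weight-bearing, and surgery are likely to affect the risk of DVT".
- On delay in applying IPC it concedes: "Moreover, patients may even suffer a VTE before treatment is initiated". Its response is a comparison of early with late enrolment.
- No baseline ultrasound for thrombus is described. Baseline values are mentioned only for femoral blood velocity.

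**The concern.** The plan expects some scans to be technically difficult, yet leaves the reviewer no way to say that a segment could not be judged. When no thrombus is visible and part of the venous tree was not seen, there is little basis for recording presence, so absence is the likely entry. A failed measurement then enters the analysis as a negative outcome. With at least 20 hospitals, silence also lets the same kind of scan be handled differently from site to site.

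The second part arises from the definition and the eligibility list, not from the difficult-scan sentence. Thrombus found at six weeks is an event whatever its age. A clot already present at randomisation could not have been prevented by IPC, yet can be counted as incident VTE.

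Both routes affect the primary endpoint. Missed thrombus shrinks the observed risk difference. Pre-existing thrombus adds events that treatment cannot influence. If scan visibility differed between arms, the difference could also be biased in either direction.

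**Working it through.** **Inputs from the documents.** 1400 patients, 10% drop-out, 28% versus 20%, alpha 0.05, 90% power (Estimated sample size and power); 1:1 allocation (Study Design). Sidedness is not stated; two-sided is assumed. Evaluable patients per arm: 1400 × 0.90 / 2 = 630.

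**Inputs that the documents do not give.** The share of scans not assessable, and the share of patients with thrombus at entry. Both are assumptions, shown as ranges.

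**The plan's own figure.** For 90% power the normal-approximation formula gives 597 per arm: 1194 / 0.90 = 1327 in total. With continuity correction it gives 622 per arm: 1244 / 0.90 = 1383, within 3% of 1400. Power at 630 per arm is Φ[(d − 1.96·√(2p̄(1−p̄)/n)) / √((p₁(1−p₁)+p₂(1−p₂))/n)] = Φ[(0.080 − 1.96 × 0.02406) / 0.02396] = Φ(1.371) = 91.5%. The sample size reproduces, and no stated figure is in dispute.

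**Incomplete scans, equal in both arms.** Assume visibility is unrelated to VTE and an unassessable scan misses any clot. Coded absent, observed risk = true risk × (1 − u). Set to missing, the risks stay at 28% and 20% and n becomes 630 × (1 − u).

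| u, both arms | Coded absent: risks | Difference | Power | Set to missing: difference | Power |
|---|---|---|---|---|---|
| 5% | 26.6% vs 19.0% | 7.6 | 89.6% | 8.0 | 90.1% |
| 10% | 25.2% vs 18.0% | 7.2 | 87.5% | 8.0 | 88.5% |
| 20% | 22.4% vs 16.0% | 6.4 | 82.3% | 8.0 | 84.6% |

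At equal rates, setting scans to missing mainly preserves the estimate. At 10% the gain in power is one point.

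**Incomplete scans, unequal between arms (no data in the documents).** Coded absent, 10% in control and 5% with IPC gives 25.2% vs 19.0%: difference 6.2 points, power 75.6%. The reverse, 5% and 10%, gives 26.6% vs 18.0%: 8.6 points. With no true effect at 28%, 5% in control and 10% with IPC gives 26.6% vs 25.2%, a spurious 1.4 points. The chance of wrongly favouring IPC rises from 2.5% to about 8%.

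**Why simple exclusion is not enough.** Segments are read separately, so a scan with an unseen calf may still show popliteal or femoral thrombus. If visible thrombus counts as an event but an otherwise negative incomplete scan is dropped, missingness depends on the outcome. Assume 30% of thromboses in incomplete scans are visible in another segment, with 10% incomplete in control and 5% with IPC:

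- Control: (0.90 × 0.28 + 0.10 × 0.28 × 0.30) / (0.90 + 0.10 × 0.28 × 0.30) = 0.2604 / 0.9084 = 28.7%.
- IPC: (0.95 × 0.20 + 0.05 × 0.20 × 0.30) / (0.95 + 0.05 × 0.20 × 0.30) = 0.1930 / 0.9530 = 20.3%.
- Difference 8.4 points from unrounded values, instead of 8.0. With the rates reversed it is 7.8.

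**Thrombus at entry in a share v of patients, equal in both arms.** If these clots add to the planned rates, risk = v + (1 − v) × planned risk. If they are already part of the 28%, IPC risk = v + (0.28 − v) × 20/28.

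| v | Added: difference | Power | Within 28%: difference | Power |
|---|---|---|---|---|
| 1% | 7.9 | 90.4% | 7.7 | 89.3% |
| 2% | 7.8 | 89.2% | 7.4 | 86.8% |
| 5% | 7.6 | 85.4% | 6.6 | 77.2% |
| 10% | 7.2 | 78.6% | 5.1 | 55.4% |

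**The case against.** A reader might infer that the plan directs unseen veins to be scored as no VTE. It does not. The physician is asked to establish the diagnosis and could call presence. The Outcome paragraph of Study Design notes that ultrasound is easily repeated, although it sets no repeat rule. The drop-out allowance and the milestone of more than 80% of primary outcomes reported (Specific intermediate objectives) show that some patients may have no outcome, so a non-diagnostic scan might be repeated or left unreported. Segment recording also follows a cited earlier trial, which may hold adequacy rules that cannot be checked here. All of this stands. It does not remove the fact that the written rule offers two results for a difficult scan.

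A reader might also infer bias towards IPC, for instance because compression and stockings change calf swelling and hence visibility. The documents give no data on visibility by arm, and the bias could run either way. The fall to about 76% power also assumes that an incomplete scan misses every clot. If 30% were visible elsewhere, the same 10%/5% case would give 6.7 points and 82%. The unequal-rate figures show sensitivity only.

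On pre-existing thrombus, randomisation should balance it on average, and the planned analyses by prior DVT and by delay show that the issue was noticed. Those analyses do not change which clots count.

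**Conclusion.** The concern holds as a defect in the endpoint rule. As written, an incompletely seen scan has to become a definite result, most naturally absence. Thrombus that predates randomisation can count as incident VTE, through the definition together with the exclusion list. The documents do not state that unseen veins are negative or that old clots are new events, and they do not support a claim of bias in a known direction.

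The expected consequence is some dilution of the risk difference. Its size is unknown. With 10% of scans not assessable in both arms the loss is modest: 0.8 points in the difference, and 87.5% power against 91.5%. For clots at entry the result depends heavily on the assumed prevalence and on whether they already form part of the 28%. These figures rest on 630 evaluable patients per arm, a two-sided 5% test, true risks of 28% and 20%, and visibility unrelated to VTE. The change is worth making because it is cheap and concerns the primary endpoint.

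**What to change.** 1. Record each vein segment as thrombus, no thrombus or not assessable. Visible thrombus in any segment is an event. A scan with no visible thrombus and any segment not assessable is a missing primary outcome, not a negative one.
2. Name the missing-data method in the Statistical analysis plan, which currently gives none: for example, multiple imputation using the segments that were seen and baseline factors. Do not simply exclude these patients, for the reason shown above.
3. Report not-assessable scans by arm, and repeat the primary analysis with not assessable coded as absent as a sensitivity analysis.
4. Add a VTE diagnosed between injury and randomisation to the exclusion list.
5. In patients with prior DVT, have the blinded physician record whether thrombus appears old or new, for a sensitivity analysis only. Without a baseline ultrasound, dating thrombus at six weeks is too unreliable to define the primary endpoint.

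The cost is an extra level and one extra field on the ultrasound form, one eligibility line and a few sentences in the Statistical analysis plan, with no new visits. A few outcomes become missing and a few patients are not enrolled. Undiagnosed clots formed before enrolment would still count, and the report should say so.

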Further patient data that will be analyzed as secondary outcome measures at 2 and 6 weeks are adherence to allocated treatment and adverse events related to IPC. Adverse events (binary) that will be registered are 1) Any damage to the skin of the legs including infection. 2) Any reasons for prematurely stopping the IPC. 3) Any fall associated with significant injury occurring within 6 weeks of enrollment. The frequency of the adverse events of each group will be presented⁹.

Health economic analyses, together with Karolinska Institutet, LIME, Med. dr. [name], of the trial treatment effects will involve a within-trial evaluation of cost effectiveness integrated into a decision-analytic model of longer run costs and health effects.

Study Design (PICO)

“STOP leg clots” is an international, multicentre prospective randomized, controlled, parallel group trial with blinded assessment of the outcome. The allocation ratio is 1:1. The study has an Ethical review board approval 2016/1753-31 and is registered at clinicaltrials.gov.

Patients: At least 20 hospitals in a minimum of twelve regions have accepted to participate, and this captures a study population, which is representative of Sweden. The included patients, ATR and ankle fractures, are representative of, and constitute a large part of the population with lower limb immobilization. Moreover, patients with ATR and AF have

demonstrated low- or non-effectiveness of LMHW prophylaxis also in relation to the risk of bleeding complications^{3 4}. Therefore, there is a need for an alternative prophylaxis with documented effects.

In the perspective that different hospitals have different clinical traditions/indications for surgery of ATR and AF we have chosen to include both operated and non-operated ATR/AF, since both groups are equally served by VTE prophylaxis. Earlier studies have shown a just as high incidence of VTE in non-operated as in operated ATR/AF⁶, further indicating a benefit of demonstrating a VTE risk reduction in both operated/non-operated lower limb immobilized patients. Surgery vs. no surgery will be accounted for in the statistical analysis.

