Intervention: There is a need for new VTE prophylactic methods, especially in lower limb immobilized patients. IPC has been demonstrated cost effective both as adjuvant and versus no pharmacoprophylaxis in hospitalized patients by NICE. However, in an outpatient setting there are yet only recent short-term data of the efficacy of IPC. There is a need for data on the efficacy of IPC during long-term leg immobilization to inform guidelines.

The intervention, *addition of IPC to routine care*, will be administered in the emergency department or in the outpatient clinic. Patients will during the six weeks of lower limb immobilization receive bilateral calf IPC (Venaflo Elite, DJO LLC, Vista, CA, USA) applied under an orthosis (Aircast® AirSelect Elite, DJO LLC, Vista, CA, USA). This IPC-system delivers rapid inflation and graduated sequential compression. The IPC device is mobile and should therefore not restrict patient mobilization, but can be taken off if the patient wants to mobilize independently. The patients will be instructed to apply the IPC-therapy continuously, both day and night. Compliance with the treatment will be registered by both the patient and by the device⁹. American College of Chest Physicians recommend that efforts should be made to achieve 18 h of daily compliance with IPC in hospitalized patients¹⁷. However, there are no recommendations for mobile outpatients. Outpatients were in our recent study recommended at least 6h daily therapy, and in this study we will increase the recommendation to 10h/daily. Graduated compression stockings are part of IPC-care and these should be applied and worn under the IPC sleeves on both legs. IPC will be discontinued if the patient declines to continue IPC or had adverse effects of the IPC that warrants removal. At the 2 and 6 weeks visit the orthosis will be removed by a nurse and the patient will be examined by an orthopaedic surgeon (masked to the treatment allocation), who will document compliance and adverse events. At the 6 weeks visit the patient will also be sent for CDU-examination, which will document the main outcome. Patients will during the six weeks leg immobilization be weight-bearing with crutches or non-weight-bearing with crutches according to the preference of the orthopedic surgeon (masked to the treatment allocation). Weight-bearing will be recorded and accounted for in the statistical analysis.

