Comparator: Since there are no documented highly effective therapies for DVT reduction during leg immobilization, and guidelines vary regarding prophylaxis, we chose to use treatment-as-usual as a comparator, regardless of LMHW use or not^{3 4}. Based on our calculations less 10% of the patients will receive LMHW in clinical practice and our power calculations has taken this into account. NICE has stated that LMWH is not a feasible general treatment, especially health economically, during six weeks for all patients with leg immobilization. One review, including 1,490 patients from six randomized trials, showed a small reduction in DVTs using LMHW⁸. However, they concluded that more research is needed to develop more effective and safe thromboprophylactic treatments. Moreover, since a study with LMHW as a comparator would necessitate too many patients - this was not an option. The main research question remains: Is adjuvant IPC more effective than routine care for reducing the incidence of VTE in patients during lower limb immobilization? The usage of no general VTE-prevention in the comparator group is moreover justified since a DVT-screening will be performed on all patients. LMWH vs. no LMWH will be accounted for in the statistical analysis. If a VTE is detected we will follow clinical guidelines and initiate

pharmacological VTE-treatment.

The comparator, **routine care**, lower limb immobilization will be administered by normal routine in the emergency department or in the outpatient clinic. Routine care include that the lower limb will be immobilized in an orthosis or a below-knee plaster cast according to local routines. At the 2 and 6 weeks visit the orthosis/plaster cast will be removed by a nurse who will document compliance. Subsequently, the patient will be examined by an orthopaedic surgeon (masked to the treatment allocation), who will document adverse events. At the 6-8 weeks visit the patient will also be sent for CDU-examination, which will document the main outcome. Patients will during the six weeks leg immobilization be weight-bearing with crutches or non-weight-bearing with crutches according to the preference of the orthopedic surgeon (blinded to the treatment group). Weight-bearing will be recorded and accounted for in the statistical analysis.

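### The surgeon described as masked is asked to record entries in the IPC arm that can reveal allocation, and one listed adverse event can occur only in that arm

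*Combined protocol and SAP*

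**What the plan says.** **IPC arm** (Study Design, Intervention). A nurse removes the orthosis at the 2- and 6-week visits, and "the patient will be examined by an orthopaedic surgeon (masked to the treatment allocation), who will document compliance and adverse events". Earlier in the same paragraph compliance refers to the device: "Compliance with the treatment will be registered by both the patient and by the device", and the guideline benchmark cited is that "efforts should be made to achieve 18 h of daily compliance with IPC in hospitalized patients".

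**Comparator arm** (Study Design, Comparator). At the same visits "the orthosis/plaster cast will be removed by a nurse who will document compliance". After that, "the patient will be examined by an orthopaedic surgeon (masked to the treatment allocation), who will document adverse events".

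**Outcomes** (Variables and measures). The secondary outcomes at 2 and 6 weeks include "adherence to allocated treatment and adverse events related to IPC". The adverse events are labelled binary. Item 1 is skin damage to the legs, including infection. Item 2 is "2) Any reasons for prematurely stopping the IPC". Item 3 is a fall with significant injury. The reporting rule is: "The frequency of the adverse events of each group will be presented".

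**Analysis and blinding.** The Statistical analysis plan presents binary outcomes, primary or secondary, as adjusted odds ratios with 95% confidence intervals and states no exemption. The list of blinded outcome assessors at the end of the patient selection section names ultrasonographers, and physiotherapists or nurses for patient-reported outcomes. It does not name the examining surgeon. It adds that patients and the clinician applying IPC are not blinded.

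**The concern.** Skin damage and falls with significant injury are harms that the plan singles out for registration, and both need some judgement. The protocol states that a masked surgeon records adverse events in both arms. If the same visit in the IPC arm requires that surgeon to write down how the device was used, or why it was stopped, the stated masking cannot be relied on for the harms recorded beside it. A report could then claim masked harm assessment that the procedure did not secure.

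A second, separate problem concerns item 2. Controls have no device to stop, so comparing the arms on this item carries no information about the effect of treatment, yet the general analysis rule calls for an odds ratio.

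**Working it through.** **1. Duties side by side at the 2- and 6-week visits**

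| | IPC arm | Comparator arm |
|---|---|---|
| Removes orthosis or cast | Nurse | Nurse |
| Documents compliance | Surgeon, called masked | Nurse |
| Documents adverse events | Surgeon, called masked | Surgeon, called masked |
| Stated order | None between compliance and adverse events | Nurse first, surgeon afterwards |

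The comparator text has a separation of roles and an order that the IPC text lacks.

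**2. What each entry reveals**

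- *Compliance, read as IPC use.* The entry reveals allocation for every IPC patient seen.
- *Compliance, read as immobilization or allocated care.* The content need not reveal allocation. The surgeon is still asked for it in one arm only, so the request is a cue.
- *Item 2.* The surgeon records adverse events in both arms, so the same three-item list can apply to everyone. A positive entry identifies an IPC patient; a negative entry reveals nothing. This route is limited to patients who stopped.

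**3. Exposure**

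Inputs (Estimated sample size and power; Study Design): 1400 patients, 10% drop-out, 1:1 allocation, two visits.

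- IPC patients after drop-out: 1400 x 0.90 / 2 = 630.
- IPC-arm surgeon visits: 630 x 2 = 1260. With no drop-out: 700 x 2 = 1400.

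This is an upper bound. It requires the IPC-use reading of compliance and an entry made before the skin and fall items. If item 2 were the only route, the count would depend on the stopping rate, which the documents do not give (the 91% from the earlier study is compliance, not persistence). Assuming 2% to 20% stop: 630 x 0.02 = 12.6, about 13 patients, up to 630 x 0.20 = 126 patients.

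These figures count opportunities for unmasking. They do not measure bias: the documents give no event or detection rates, so neither its size nor its direction can be calculated.

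**4. Item 2 under the odds-ratio rule**

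Let *a* of 630 IPC patients and 0 of 630 controls have the event. The odds ratio is

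(a x 630) / (0 x (630 - a)),

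which has a zero denominator for any *a* above 0. In the logistic model the likelihood keeps rising as the arm coefficient grows. In an illustrative fit with *a* = 6, the coefficient rose by about 10 for every ten further Newton steps, and its standard error grew without limit. Adding a simulated binary covariate did not change this. If a few controls crossed over to IPC an estimate might exist, but it would still describe who had a device.

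**The case against.** **Compliance may not mean IPC use.** The comparator text uses the word at the same visits for patients with no device, where it must mean immobilization or allocated care, and IPC hours already come from the patient and the device. This stands in part. The IPC reading is the more natural one in its own paragraph but not the only one, so the exposure figure is a ceiling.

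**Item 2 is a narrow route.** This stands: it reveals allocation only for patients who stopped.

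**Patients are unblinded and may tell the surgeon anyway.** True, but occasional disclosure differs from a recording duty that can reveal allocation at every IPC visit.

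**Item 2 may only be tabulated.** The adverse event paragraph speaks of presenting frequencies. A reader might infer that the plan will test item 2 and declare a significant harm. The documents propose no such test and do not say that adverse event items will be pooled. The difficulty arises only if the general odds-ratio rule is applied to this item, which the text does not rule out.

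**Stronger reading: the primary outcome is compromised.** The documents do not support this. Masked ultrasonographers perform the screening scan, and a blinded vascular physician reviews positive and technically difficult examinations. It would also go too far to call the primary analysis wholly untouched. A surgeon called masked chooses weight-bearing, which is a covariate in the logistic model, but the text does not say that this is the same surgeon. The masking statements for the primary outcome concern ultrasound and do not say who reads the CT for pulmonary embolism. Neither point shows bias.

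**Conclusion.** The plan should be changed here. As written, masked recording of skin damage, infection and injurious falls is not protected in the IPC arm, because the surgeon called masked is given a compliance duty there that the nurse has in the comparator arm. Full exposure (at most 1260 visits after the planned drop-out) assumes that compliance means IPC use; the unequal duties remain a cue on either reading. No claim can be made about how large any bias would be or which arm it would favour.

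The main consequence is for secondary safety outcomes. Compliance also feeds an additional analysis of the primary outcome, but patient and device records supply IPC use independently of the surgeon.

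Item 2 has no finite odds ratio if the control count is zero, which holds barring crossover. Any contrast between the arms on it is not a treatment effect.

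The omission of the surgeon from the list of blinded assessors is a minor inconsistency by itself, since the Intervention and Comparator text already calls the surgeon masked. It matters because that list does nothing to settle the conflict.

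**What to change.** 1. Use the comparator arm's split and order in both arms. The nurse who removes the orthosis or cast records compliance and, for IPC patients, any discontinuation and its reason, on a form that the surgeon does not see. The surgeon then completes one identical form in both arms, covering skin damage or infection and falls with significant injury.
2. Report item 2 descriptively, in the IPC arm only, and exempt it from the odds-ratio rule in the Statistical analysis plan.
3. Reconcile the Intervention and Comparator text and the list of blinded assessors on whether the surgeon is masked. If step 1 is not adopted, remove the masking claim for the surgeon and report these harms as assessed unmasked.

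The cost is mainly in forms and wording, since a nurse already attends these visits in both arms. There are two drawbacks. A skin event that leads to stopping IPC may appear on both forms and must be linked at data entry, to avoid loss or double counting. Unblinded patients may also still disclose their allocation, so masking is improved but not guaranteed.
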